1.1.2. Secondary Objectives

The secondary objectives of the study are: To evaluate the bleeding risk (i.e., major and clinically relevant non-major [CRNM] bleeding) of REGN9933 after unilateral TKA through time of venography, compared to enoxaparin

- To assess overall safety and tolerability of REGN9933 in participants undergoing TKA
- To evaluate the efficacy of REGN9933 in prevention of clinically relevant VTE, compared to enoxaparin
- To evaluate the efficacy of REGN9933 in prevention of DVT detected by venography, compared to enoxaparin
- To evaluate the pharmacokinetics (PK) of REGN9933 after single intravenous (IV) administration
- To assess pharmacodynamic (PD) effects of REGN9933 on intrinsic and extrinsic coagulation pathways (i.e., aPTT, PT)
- To assess immunogenicity following a single dose of REGN9933 over time
- To compare the efficacy of enoxaparin and apixaban in prevention of VTE after unilateral TKA

1.2. Exploratory Objectives

The exploratory objectives of the study are:

- Explore the efficacy of REGN9933 in prevention of VTE after unilateral TKA through the end of study, compared to enoxaparin and apixaban
- Explore the efficacy of REGN9933 in prevention of symptomatic, clinical thrombosis, compared to enoxaparin and apixaban
- Explore the efficacy of REGN9933 in prevention of DVT detected by venography, compared to apixaban
- Explore the extent of DVT burden on venography in participants receiving REGN9933 compared to enoxaparin and apixaban
- Explore the bleeding risk (i.e., major bleeds and CRNM) of REGN9933 after unilateral TKA through end of study compared to enoxaparin and apixaban
- Explore the occurrence of minor bleeding compared to enoxaparin and apixaban
- Explore biomarkers related to FXI inhibition by REGN9933
- Develop a molecular understanding of venous thromboembolism, and related diseases
- Explore relationships between PK, biomarkers of anticoagulant activity, and efficacy
- To study REGN9933 mechanism of action the coagulation cascade, VTE, and related diseases

- Explore whether potential differences in participant efficacy and safety are associated with genotype and gene expression and further study FXI and coagulation-related diseases, using optional whole blood DNA and RNA collected from consented participants

1.3. Statistical Hypothesis

The clinical hypothesis comparing the efficacy of REGN9933 to enoxaparin or apixaban will be assessed through a Bayesian estimation framework. Bayesian posterior probabilities will be reported to estimate the incidence of confirmed VTE for participants treated with REGN9933 and enoxaparin, as well as the odds ratio (OR) of confirmed VTE in participants administered REGN9933 as compared to that of enoxaparin (OR_{RE}). The statistical hypothesis $OR_{RE} < 1$, i.e. that incidence of confirmed VTE is lower in the REGN9933 arm compared to the enoxaparin arm.

1.4. Modifications from the Statistical Section in the Final Protocol

There is no modification from the statistical section in the final protocol.

1.5. Revision History for SAP Amendments

This is the original version of the SAP.

2. INVESTIGATION PLAN

2.1. Study Design

The study consists of the following periods: a screening period (day -30 to day -1) and a 75-day open-label treatment and follow-up period with REGN9933 or enoxaparin or apixaban.

Participants who are at least 50 years of age and undergoing elective, unilateral TKA will be randomized after surgery to one of 3 treatment arms—REGN9933, enoxaparin, apixaban—in a ratio of 1:1:1, in a parallel manner. Randomization will be stratified based on study site and age (<70 vs \geq 70 years of age). Approximately 120 participants will be enrolled in each arm, for a total of up to approximately 360 participants in the study.

After providing informed consent, participants will undergo screening, which can occur from approximately day -30 to -1 (day 1 is defined as the day of TKA surgery). Participants will be randomized after completion of surgery to treatment in one of the following groups:

[figure not shown]
- REGN9933 300 mg IV, once
- Enoxaparin 40 mg subcutaneous (SC), daily through the time of venography or day 12, whichever is earlier
- Apixaban 2.5 mg orally (PO), BID, daily through the time of venography or day 12, whichever is earlier

Dosing with REGN9933 will occur 12 to 24 hours after the end of surgery.

Dosing with enoxaparin or apixaban will begin 12 to 24 hours after the end of surgery and will continue through the day of venography (or day 12, whichever is earlier). Administration of enoxaparin prior to TKA surgery is not permitted in this study (see protocol Section 7.2.2 Exclusion criterion 10 and Section 8.8.1). All investigators must comply and satisfy all requirements for the local risk management plan or equivalent for apixaban and enoxaparin where applicable and before dosing participants.

Below is the study flow diagram depicting the different periods of the study with the scheduled visits and treatment administrations.

Figure 1: Study Flow Diagram

2.2. Sample Size and Power Considerations

Approximately 360 participants will be randomized in a 1:1:1 allocation ratio to REGN9933, apixaban or enoxaparin. Each arm will have approximately 120 participants.

The sample size was determined through Bayesian approach. The treatment difference was expressed as the log(OR), and the prior distribution of the treatment difference was assumed to be $N(0,0.843)$, which follows a normal distribution centered around no treatment difference and with a variance such that extreme treatment differences are expected to be unlikely, i.e., 90% probability that OR is between 0.25 and 4.0.

The probability of any beneficial effect of REGN9933 over enoxaparin can be assessed by the posterior distribution of the odds ratio comparing REGN9933 to enoxaparin of confirmed VTE. A beneficial effect is where $OR_{RE} < 1$, and thus the study will estimate $Prob(OR_{RE} < 1 | \text{data})$.

The sample size of 120 patients per arm was determined through 10000 trial simulation, assuming confirmed VTE event rates of 13% for REGN9933 and 22.4% for enoxaparin. (Enoxaparin rates taken from [\(Verhamme, 2021\)](#) [\(Weitz, 2020\)](#)). Out of the 10000 simulated trials, 75% of the simulated trials with $Prob(OR_{RE} < 1 | \text{data}) > 0.95$ have the sample size of 120 or less.

3. ANALYSIS SETS

The following defines the set(s) of participants whose data will be used for statistical analysis.

3.1. Efficacy Analysis Set

The primary analysis will be conducted in the modified intention to treat population (mITT) population, consisting of randomized and treated participants that have either an evaluable venogram, a confirmed episode of venous thromboembolism, or both through day 12. It is based on the treatment allocated (as randomized).

3.2. Safety Analysis Set

The safety analysis set (SAF) includes all randomized participants who received any study drug; it is based on the treatment received (as treated). Treatment compliance/administration and all clinical safety variables will be analyzed using the SAF.

3.3. Pharmacokinetic Analysis Set

The pharmacokinetic analysis set (PK) includes all participants in the REGN9933 treatment group who received study drug and who had at least 1 non-missing result following the first dose of study drug.

3.4. Immunogenicity Analysis Sets

The ADA analysis set (AAS) includes all participants who received study drug (REGN9933) and had at least 1 non-missing ADA result following the first study dose.

3.5. Pharmacodynamic Analysis Sets

The pharmacodynamic analysis set (PDAS) includes all randomized participants who received any study drug and who had at least 1 non-missing PD result following the first dose of study drug; it is based on the treatment received (as treated).

4. ANALYSIS VARIABLES

4.1. Demographic and Baseline Characteristics

The following demographic variables will be summarized by treatment group:

- Age at screening (year)
- Age categories (<70, \geq 70)
- Sex (Male, Female)
- Race (American Indian/Alaskan Native, Asian, Black/African American, Native Hawaiian/Other Pacific Islander, White and Other)
- Ethnicity (Hispanic/Latino, Not Hispanic or Latino)
- Weight (kg)
- Height (cm)
- Body mass index (BMI) (kg/m²)

Other baseline characteristics may include:

- Medication history (antiplatelets; NSAIDs; hormone replacement therapy)
- aPTT (sec)
- PT (sec)
- FXI functional activity level
- TKA information (including but not limited to operative leg, blood loss during surgery, and type of anesthesia)

4.2. Medical History

Medical histories will be coded to a Preferred Term (PT) and associated primary System Organ Class (SOC) according to the latest available version of the Medical Dictionary for Regulatory Activities (MedDRA).

4.3. Prior / Concomitant Medication

Any treatment administered from the time of informed consent to the final study visit will be considered concomitant medication. This includes medications that were started before the study and are ongoing during the study.

Medications will be recorded from the day of informed consent until the end of study (EOS) visit. Medications will be coded to the anatomical therapeutic chemical (ATC) classification level 2 (therapeutic main group) and ATC level 4 (chemical/therapeutic subgroup), according to the latest available version of WHO Drug Dictionary (WHODD). Participants will be counted once in all ATC categories linked to the medication.

Prohibited concomitant medications/procedures

Administration of enoxaparin prior to TKA surgery is prohibited (see protocol Section 7.2.2 Exclusion criterion 10, and Section 8.8.1).

Anti-platelet therapy (except low doses of Acetylsalicylic acid (ASA) \leq 100 mg/day) is prohibited, unless indicated for treatment of an adverse event (AE).

The following procedures/devices are prohibited after study drug has started:

- Use of spinal or epidural analgesia post-operatively
- Pneumatic compression devices

Participants are prohibited from donating blood products through the EOS visit. Participants are prohibited from donating sperm through the EOS visit. Participants are prohibited from having planned, elective surgeries (except for TKA performed on day 1) through the EOS visit.

For participants assigned to the REGN9933 treatment arm, anticoagulant medications (including, but not limited to, vitamin K antagonists, heparins, DOACs) are prohibited after study drug has been started, unless they are indicated for treatment of an AE.

4.4. Efficacy Variables

4.4.1. Primary Efficacy Variable

The primary endpoint is adjudicated, confirmed VTE through day 12. This composite endpoint consists of: asymptomatic deep DVT detected by unilateral venography of the operated leg; confirmed symptomatic DVT of either leg; confirmed fatal or nonfatal pulmonary embolism (PE) including unexplained death for which PE cannot be ruled out.

Adjudicated VTE outcomes are generated by the Adjudication Committee that will review and determine interpretation and/or classification in a blinded manner.

4.4.2. Secondary Efficacy Variables

- Incidence of major VTE through day 12 (REGN9933 versus enoxaparin). Major VTE includes: proximal DVT; confirmed symptomatic DVT of either leg; confirmed fatal or nonfatal PE including unexplained death for which PE cannot be ruled out
- Incidence of DVT as measured by venography of the operated leg on day 10 ± 2 days (REGN9933 vs enoxaparin)
- Incidence of confirmed, adjudicated VTE through day 12 (exoxaparin vs apixaban)

4.4.3. Exploratory Efficacy Variables

- Incidence of confirmed VTE through day 12 (REGN9933 vs apixaban) and through the end of study
- Incidence of major VTE through the end of study

- Incidence of confirmed symptomatic DVT in either leg through day 12 or through the end of the study
- Incidence of confirmed PE through day 12 and through the end of study
- Incidence of fatal PE, which includes sudden death for which PE cannot be ruled out, through day 12 and through the end of study
- Incidence of DVT as measured by venography of the operated leg on day 10 ± 2 days (REGN9933 vs apixaban)
- In participants with DVT detected on venogram:
 - distribution of DVT (proximal versus distal)
 - for proximal DVT, size of VTE
 - for distal DVT, the number of veins affected

4.5. Safety Variables

The safety variables include physical examination, vital signs, electrocardiograms (ECGs), laboratory evaluations (hematology, chemistry, urinalysis, other laboratory tests), concomitant medications, bleeding events (major bleeding and CRNM bleeding), and AEs.

4.5.1. Adverse Events and Serious Adverse Events

AEs and serious adverse events (SAEs) will be collected from the time of informed consent signature and then at each visit until the end of the study. All adverse events are to be coded to a PT and associated primary SOC according to the latest available version of MedDRA.

An AE is any untoward medical occurrence in a participant administered a study drug which may or may not have a causal relationship with the study drug. Therefore, an AE is any unfavorable and unintended sign (including abnormal laboratory finding), symptom, or disease which is temporally associated with the use of a study drug, whether or not considered related to the study drug([ICH, 1994](#))

For studies with participant reported outcomes (PRO), the PRO data are generally not reportable as individual AEs and thus will not be reported or reconciled as such.

An SAE is any untoward medical occurrence that at any dose:

- Results in **death** – includes all deaths, even those that appear to be completely unrelated to study drug (e.g., a car accident in which a participant is a passenger).
- Is **life-threatening** – in the view of the investigator, the participant is at immediate risk of death at the time of the event. This does not include an AE that had it occurred in a more severe form, might have caused death.
- Requires in-patient **hospitalization** or **prolongation of existing hospitalization**. Inpatient hospitalization is defined as a hospital admission (any duration), or an emergency room visit for longer than 24 hours. Prolongation of existing hospitalization is defined as a hospital stay that is longer than was originally anticipated for the event

or is prolonged due to the development of a new AE as determined by the investigator or treating physician.

- Results in persistent or significant **disability/incapacity** (substantial disruption of one's ability to conduct normal life functions).
- Is a **congenital anomaly/birth defect**.
- Is an **important medical event** - Important medical events may not be immediately life-threatening or result in death or hospitalization but may jeopardize the participant or may require intervention to prevent one of the other serious outcomes listed above (e.g., intensive treatment in an emergency room or at home for allergic bronchospasm; blood dyscrasias or convulsions that do not result in hospitalization; or development of drug dependency or drug abuse).

Criteria for reporting SAEs must be followed for these events as per study protocol.

An adverse event of special interest (AESI) (serious or non-serious) is one of scientific and medical interest specific to the sponsor's product or program, for which ongoing monitoring and rapid communication by the investigator to the sponsor can be appropriate. Such an event might warrant further investigation in order to characterize and understand it.

Adverse Events of Special Interest for this study are:

- Moderate or severe infusion reactions
- Moderate or severe hypersensitivity reactions potentially related to study treatment
- Moderate to severe bleeding (both spontaneous and non-spontaneous)

4.5.2. Bleeding Events

The ISTH criteria will be used for both major bleeding events and CRNM events as described below. Minimal bleeding will be captured separately as an exploratory endpoint.

Major bleeding, CRNM bleeding and minimal bleeding through time of venography (or day 12, whichever is earlier) and through the end of study will be summarized by each treatment group.

Major Bleeding (ISTH):

- Fatal bleeding and/or
- Bleeding that is symptomatic and occurs in a critical area or organ, such as intracranial, intraspinal, intraocular, retroperitoneal, pericardial, in a non-operated joint, or intramuscular with compartment syndrome, assessed in consultation with the surgeon, and/or
- Overt extra surgical site bleeding causing a fall in hemoglobin level of 20 g/L (1.24 mmol/L) or more, or leading to transfusion of two or more units of whole blood or packed red cells, with temporal association within 24 to 48 hours to the bleeding, and/or
- Surgical site bleeding that requires a second intervention (open, arthroscopic, endovascular) or a hemarthrosis of sufficient size as to interfere with rehabilitation by delay

in mobilization or delayed wound healing, resulting in prolonged hospitalization or a deep wound infection, and/or

- Surgical site bleeding that is unexpected and prolonged and/or is sufficiently large to cause hemodynamic instability, as assessed by the surgeon. There should be an associated fall in hemoglobin level of at least 20 g/L (1.24 mmol/L), or transfusion indicated by the bleeding, of at least two units of whole blood or red cells, with temporal association within 24 hours to the bleeding.

Clinically Relevant Non-Major Bleeding (ISTH):

- Any sign or symptom of hemorrhage (e.g., more bleeding than would be expected for a clinical circumstance, including bleeding found by imaging alone) that does not fit the criteria for the ISTH definition of major bleeding but does meet at least one of the following criteria:
 - requiring medical intervention by a healthcare professional
 - leading to hospitalization or increased level of care
 - prompting a face to face (i.e., not just a telephone or electronic communication) evaluation

Minimal Bleeding:

Any overt bleeding event that does not meet the criteria for either major or CRNM bleeding will be categorized as a minor bleeding event. Minimal bleeding will be captured separately as an exploratory endpoint.

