4.1.2. Secondary Endpoints

The secondary endpoints are:

- Incidence of major bleeding and CRNM bleeding (defined in Section 5.3.1) through time of venography (or day 12, whichever is earlier)
- Incidence of treatment-emergent adverse events (TEAEs) through the end of study
- Incidence of major VTE (defined in Section 5.2.2) through day 12 (REGN9933 versus enoxaparin)
- Incidence of DVT as measured by venography of the operated leg on day 10 ± 2 days (REGN9933 vs enoxaparin)
- Concentrations of REGN9933 in serum through end of study
- Change in aPTT from baseline through end of study
- Change in PT from baseline through end of study
- Incidence and titer of anti-drug antibodies (ADA) to REGN9933 through end of study
- Incidence of confirmed, adjudicated VTE through day 12 (enoxaparin vs apixaban)

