11.4.5. Safety Analysis

Safety will be assessed by clinical and statistical review of all relevant parameters, including vital signs, physical examinations, ECGs, laboratory evaluations, and AEs.

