5. STATISTICAL METHODS

Unless otherwise stated, the following conventions will be applied when presenting summary level statistics for data.

Continuous variables will be summarized within each treatment group, presenting the following descriptive statistics: the number of participants reflected in the calculation (n), average, sample standard deviation (SD), median, minimum, maximum, 1st quartile and 3rd quartile.

Categorical or ordinal data will be summarized within each treatment group by frequency (i.e. total number of observations within each level of the categorical variable in a given treatment group) and percentages. All levels of the categorical variable will be included. If there are observations where the level of the categorical variable is missing, a separate category titled “Missing” will be created. For categorical variables that are ordinal in nature, the order in which the levels of the categories are displayed will be consistent with the natural ordering of the category levels. Percentages will also be calculated for each level of the categorical variables with respect to the total sample size for the respective treatment arm.

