5.7.2. Analysis of Secondary and Exploratory Efficacy Variables

Unless otherwise specified, categorical efficacy endpoints (defined in Section [4.4.2](#) and Section [4.4.3](#)) will be analyzed by Bayesian logistic regression models in a similar manner for the primary efficacy variable on the mITT set.

Bayesian summary statistics (posterior mean and median, and two-sided 90% credible interval) of the treatment effect (odds ratio) will be reported.

For the exploratory analyses, the distribution of DVT (proximal versus distal) will be summarized descriptively for participants detected on venogram. Proximal DVT will be characterized by the size of the venous thromboembolism (VTE), while distal DVT will be summarized by the number of affected veins.

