5.8.2. Assessment for Bleeding

Participants will be assessed for surgical site bleeding events at time points according to [Table 3](#). Description of surgical site bleeding events will include the following: onset and duration; associated clinical symptoms (if any) and sequelae, including prolonged hospitalization or deep wound infection; requirement for additional surgical or interventional procedure.

Participants will also be assessed for overall bleeding events at time points according to [Table 3](#). Description of bleeding events will include the following: location; onset and duration; associated symptoms (if any); precipitating factors (if any).

For all bleeding events (surgical and extra surgical), the following will be recorded: associated changes in hemoglobin, hematocrit; requirement for, timing of, and quantity of transfusion.

In addition, for all participants, peri- and post-operative blood loss will be recorded, as per local practice.

All bleeding events will need to be recorded as an AE with documentation sent to the central AC as instructed in the Study Manual for Venography and Event Reporting. Events will be classified by the AC using the ISTH criteria for both major ([Schulman, 2010](#)) and CRNM ([Kaatz, 2015](#)) bleeds as described in [Section 4.5.2](#).

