11. APPENDIX

11.1. Summary of Statistical Analyses

Table 1: Efficacy/PD Analyses

Endpoint	Analysis Populations	Primary Statistical Method/Analysis	Sensitivity Analysis	Subgroup Analysis	Other Analyses
Primary Endpoint					
Proportions of participants with adjudicated, confirmed VTE through day 12	mITT	Bayesian logistic regression	Stratified CMH analysis	Yes	No
Secondary/PD Endpoints					
Secondary efficacy endpoints	mITT	Bayesian logistic regression	Stratified CMH analysis	Yes	No
aPTT, PT	PDAS	Descriptive Statistics	No	No	No
FXI:C, TGA	PDAS	Descriptive Statistics	No	No	No

Table 2: Safety Analyses

Endpoint	Analysis Populations	Statistical Method	Supportive Analysis	Subgroup Analysis	Other Analyses
Adverse Events	SAF	Descriptive Statistics	No	No	No
Laboratory Measures	SAF	Descriptive Statistics	No	No	No
Vital Signs	SAF	Descriptive Statistics	No	No	No
ECG	SAF	Descriptive Statistics	No	No	No

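### Bleeding relative to enoxaparin is the first secondary objective, but neither document pre-specifies a between-arm bleeding estimate or interval; the SAP plans per-arm summaries only

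*SAP*

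**What the plan says.** **Objective.** Protocol 2.2 and SAP 1.1.2 list first among the secondary objectives the bleeding risk, defined as major and CRNM bleeding, "of REGN9933 after unilateral TKA through time of venography, compared to enoxaparin".

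**Endpoint.** Protocol 4.1.2 words the matching endpoint as "Incidence of major bleeding and CRNM bleeding (defined in Section 5.3.1) through time of venography (or day 12, whichever is earlier". It names no comparator. In the same list, both REGN9933 efficacy endpoints (major VTE and venographic DVT) name enoxaparin as the comparator.

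**Analysis.**
- SAP 4.5.2: major, CRNM and minimal bleeding, up to venography or day 12 and "through the end of study will be summarized by each treatment group".
- SAP 5: "Categorical or ordinal data will be summarized within each treatment group by frequency" and percentage.
- SAP 5.8.2, the bleeding section of the methods chapter, describes what is recorded and how it is adjudicated ("Events will be classified by the AC using the ISTH criteria for both major" and CRNM bleeds). It names no estimator.
- SAP 5.7.2: the categorical efficacy endpoints of 4.4.2 and 4.4.3 "will be analyzed by Bayesian logistic regression models in a similar manner for the primary efficacy variable on the mITT set", with odds ratios and 90% credible intervals. Bleeding is defined in 4.5.2, outside that scope.
- SAP 11.1, "Table 2: Safety Analyses": rows for adverse events, laboratory measures, vital signs and ECG, all descriptive. There is no bleeding row.
- Protocol 11.4.5: "Safety will be assessed by clinical and statistical review of all relevant parameters", followed by adverse event tables.

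**The concern.** The objective asks a comparative question, and the planned analysis answers a descriptive one. The efficacy side of the same SAP gets between-arm odds ratios with intervals. The leading safety objective gets neither, although SAP 5.7.5 says that the study's inference is about estimation.

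The protocol's introduction presents factor XI inhibition as a way to keep antithrombotic efficacy with less bleeding, so the bleeding comparison will be read closely. If events are few, two small percentages side by side can be read as showing no extra bleeding when the data leave an excess of several points open. Without a pre-specified measure, window, composite and interval method, those choices would also be made after the data are in, in an open-label trial.

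**Working it through.** **1. Is a between-arm bleeding estimate specified anywhere?** I set the sections side by side.

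| Place | Gives for bleeding | Between-arm measure? |
|---|---|---|
| Protocol 2.2, SAP 1.1.2 | Objective, relative to enoxaparin | Comparison intended, no measure |
| Protocol 4.1.2 | Incidence | None |
| SAP 4.5.2 | Summary by arm, two windows | None |
| SAP 5 | Default for categorical data: frequency and percentage within arm | None |
| SAP 5.7.2 | Model for the 4.4.2 and 4.4.3 efficacy endpoints, mITT set | Does not reach 4.5.2 |
| SAP 5.8.2 | Recording and adjudication | None |
| SAP 11.1, Table 2 | No bleeding row; all rows descriptive | None |
| Protocol 11.4.5 | General review and adverse event tables | None |

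The answer is no. Neither Protocol 4.1.2 nor SAP 4.5.2 says whether major and CRNM bleeding form one composite.

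**2. The plan's own figures.** There is none for bleeding to reproduce. The 120 per arm in Protocol 11.2 and SAP 2.2 was chosen from VTE rates alone (13% and 22.4%).

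**3. What an interval would show.** The inputs are n = 120 per arm (SAP 2.2) and event counts that I assume. For each arm, p = x/n, and (l, u) is the Wilson 95% interval. With arm 1 = REGN9933, arm 2 = enoxaparin and d = p1 - p2, the Newcombe limits are:

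- lower = d - sqrt[(p1 - l1)² + (u2 - p2)²]
- upper = d + sqrt[(u1 - p1)² + (p2 - l2)²]

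*Worked case, 2 vs 5 events (in %).* p1 = 1.67 (0.46 to 5.87), p2 = 4.17 (1.79 to 9.38), d = -2.50.
- Lower: -2.50 - sqrt(1.21² + 5.21²) = -2.50 - 5.35 = -7.85 (-7.86 with unrounded limits).
- Upper: -2.50 + sqrt(4.20² + 2.38²) = -2.50 + 4.83 = 2.33.

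*Worked case, 0 vs 0.* The Wilson upper limit is 1.96²/(120 + 1.96²) = 3.84/123.84 = 3.1%, so the interval is ±3.1 points.

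| Assumed events, REGN9933 vs enoxaparin | Difference (points) | Newcombe 95% interval |
|---|---|---|
| 0 vs 0 | 0 | -3.1 to 3.1 |
| 1 vs 1 | 0 | -3.8 to 3.8 |
| 2 vs 2 | 0 | -4.4 to 4.4 |
| 2 vs 5 | -2.5 | -7.9 to 2.3 |
| 6 vs 6 | 0 | -6.1 to 6.1 |

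Miettinen-Nurminen intervals are close: ±3.1 at 0 vs 0, -8.0 to 2.2 at 2 vs 5, and ±6.2 at 6 vs 6.

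**4. Why a small-sample method.** The simple Wald half-width is 1.96 × sqrt[2p(1 - p)/120]. It gives 0 at 0 vs 0. At 1 vs 1 (p = 0.00833) it gives 1.96 × 0.01174 = 2.3 points, against 3.8 above. At 6 vs 6 (p = 0.05) it gives 5.5, against 6.1. It is too narrow where events are fewest.

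**The case against.** **Phase 2 safety is usually descriptive, and the SAP matches the endpoint as written.** The second half is correct: the endpoint in Protocol 4.1.2 names no contrast, and SAP 4.5.2 follows it. The mismatch therefore starts in the protocol, between objective and endpoint, and is not the SAP's alone. The objective is still comparative, and an estimate with an interval fits the SAP's stated aim without a test, a power claim or a multiplicity adjustment.

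**The comparison can be worked out anyway.** A reader might infer that the trial will yield no comparative bleeding information, or that bleeding is left out of the reporting. The documents do not support either reading. Adjudicated bleeding will be reported by arm for both windows, and SAP 5.8 puts safety analyses on the safety analysis set, so a crude difference and an interval follow by arithmetic. All bleeding events are also recorded as adverse events, and moderate to severe bleeding is tabulated as an event of special interest. What those tables lack is the adjudicated ISTH categories and a contrast.

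**The IDMC watches bleeding relative to enoxaparin (Protocol 3.3.1).** It does, but that is oversight during the trial and supplies no study result.

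**The choice of measure is a preference.** In part, yes. An odds ratio under the SAP's prior can also be computed: at 2 vs 5 events, without covariates, the posterior median is 0.60 with a 90% credible interval of 0.23 to 1.56. However, the SAP's country-adjusted model with vague priors may be unstable at such counts, so an unadjusted estimate is safer.

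**The fix cannot add precision.** Correct. Sample size sets the width; the fix makes it visible.

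**Conclusion.** The point holds as a gap in pre-specification. The plan states a comparative bleeding objective and then a method, per-arm description, that does not by itself answer it. No between-arm measure or interval is fixed, and it is not stated whether major and CRNM bleeding are combined.

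For size: at 120 per arm, even no events in either arm would leave an excess of about 3 points compatible with the data, and a favourable-looking 2 vs 5 would leave about 2. These figures rest on assumed counts, because the documents give no bleeding rate, and on all 120 per arm being in the safety analysis set. The documents set no margin for an acceptable excess, so the figures show imprecision only and do not say that any particular excess matters clinically.

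No primary conclusion changes. This is a modest correction, worth making before database lock.

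**What to change.** **In SAP 5.8.2 and Table 2**, on the safety analysis set, pre-specify:
- the outcome: adjudicated major plus CRNM bleeding as an explicitly stated composite, and each component separately, through venography or day 12, whichever is earlier;
- the estimate: the unadjusted risk difference, REGN9933 minus enoxaparin, with a 95% Miettinen-Nurminen or Newcombe interval, naming the one chosen.

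**As exploratory**, report the same contrast for REGN9933 against enoxaparin and against apixaban through end of study. That is the window of the exploratory bleeding objective in Protocol 2.3 and the endpoint in 4.1.3.

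**Endpoint wording.** Have the SAP text say that the contrast serves the comparative objective, since Protocol 4.1.2 does not name one.

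**Cost.** One paragraph, one row in Table 2 and one output table. No new data or participants are needed. The downside is a table of wide intervals.
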